#### 8.2.1.5 ADVERSE EVENT REPORTING

When an AE/SAE occurs, it is the responsibility of the Investigator to review all documentation (eg, hospital progress notes, laboratory reports, and diagnostics reports) related to the event.

The Investigator will then record all relevant AE/SAE information (including event term, start and stop dates, severity, relationship to study treatment, outcome, if serious or non-serious) in the eCRF. Each event must be recorded separately.

It is not acceptable for the Investigator to send photocopies of the subject's medical records to the pharmacovigilance unit in lieu of completion of the AE/SAE eCRF page.

There may be instances when copies of medical records for certain cases are requested by the pharmacovigilance unit. In this case, all subject identifiers, with the exception of the subject number, will be redacted on the copies of the medical records before submission to the pharmacovigilance unit.

The Investigator will attempt to establish a diagnosis of the event based on signs, symptoms, and/or other clinical information. Whenever possible, the diagnosis (not the individual signs/symptoms) will be documented as the AE/SAE.

The Investigator is obligated to perform or arrange for the conduct of supplemental measurements and/or evaluations as medically indicated or as requested by the pharmacovigilance unit to elucidate the nature and/or causality of the AE or SAE as fully as possible. This may include additional laboratory tests or investigations, histopathological examinations, or consultation with other health care professionals.

New or updated information will be recorded in the originally completed eCRF.

#### 8.2.1.6 SERIOUS ADVERSE EVENT REPORTING

Prompt notification by the Investigator to the pharmacovigilance unit of an SAE is essential so that legal obligations and ethical responsibilities towards the safety of subjects and the safety of a study treatment under clinical investigation are met. All SAEs will be recorded and reported to the pharmacovigilance unit within 24 hours of awareness. The Investigator will submit any updated SAE data to the pharmacovigilance unit within 24 hours of receipt of the information as outlined in the Safety Reporting Instructions that will be provided to the study sites and in the study Safety Management Plan.

The pharmacovigilance unit will inform the Medical Monitor, AnaptysBio, and Innovaderm within 1 business day of awareness of a new SAE. The pharmacovigilance unit will process and evaluate all SAEs as soon as the reports are received. For each SAE received, the pharmacovigilance unit, in consultation with AnaptysBio if needed, will make a determination as to whether the criteria for expedited reporting to relevant regulatory authorities have been met.

AnaptysBio or designee has a legal responsibility to notify both the local regulatory authority and other regulatory agencies about the safety of a study treatment under clinical investigation. or designee will comply with country specific regulatory requirements relating to safety reporting to the regulatory authority, IRB/EC, and Investigators.

Investigator safety reports must be prepared for suspected unexpected SAEs according to local regulatory requirements and pharmacovigilance unit policy, and forwarded to Investigators as necessary.

An Investigator who receives an Investigator safety report describing an SAE or other specific safety information (eg, summary or listing of SAEs) from the pharmacovigilance unit will review and then file it along with the IB and will notify the IRB/EC, if appropriate according to local requirements.

If a subject dies while participating in the study, the Investigator will provide the pharmacovigilance unit with a copy of any postmortem findings.

#### **8.2.1.6.1 REPORTING VIA AN ELECTRONIC DATA COLLECTION TOOL**

---

The primary mechanism for reporting an SAE to the pharmacovigilance unit will be the electronic data capture (EDC) clinical database.

If the electronic system is unavailable, then the study site will use the back-up paper SAE Report Form. The study site will then enter the SAE data into the EDC system as soon as it becomes available.

After the study is completed and the database is locked, the toolled system will be taken off-line to prevent the entry of new data or changes to existing data.

If a study site receives a report of a new SAE from a subject or receives updated data on a previously reported SAE after the EDC system is locked, then the study site can report this information on a paper SAE form and email the form to the pharmacovigilance unit.

Contacts for SAE reporting can be found in SAE form and Safety Reporting Instructions that will be provided to the study sites.

#### **8.2.1.6.2 REPORTING VIA PAPER CASE REPORT FORM**

---

In rare circumstances, and in the absence of EDC or email, notification by telephone is acceptable for notifying the pharmacovigilance unit of an SAE. Once the EDC is available, the SAE must be reported in the system within 24 hours of it becoming available.

Initial notification via telephone does not replace the need for the Investigator to complete and sign the SAE CRF pages within the designated reporting time frames.

Contacts for SAE reporting can be found in Safety Reporting Instructions that will be provided to the study sites.

---

#### **8.2.1.7 REPORTING EVENTS TO SUBJECTS**

Not applicable.

---

#### **8.2.1.8 REPORTING OF PREGNANCY**

If a female subject or a female partner of a male subject becomes pregnant during the study and up to 28 days after the end of the study, the subject should inform the study site as soon as possible.

If a pregnancy is reported, the Investigator should inform the pharmacovigilance unit within 24 hours of learning of the pregnancy and should follow the procedures outlined in [Appendix 1](#).

If a pregnancy occurs, it will be followed up to determine the outcome, but no longer than 6 to 8 weeks after the estimated delivery date, where consent has been obtained to do so.

Abnormal pregnancy outcomes (eg, spontaneous abortion, fetal death, stillbirth, congenital anomalies, and ectopic pregnancy) are considered SAEs and must be reported within 24 hours of awareness as described in [Section 8.2.1.6](#).

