**Contraception and pregnancy:**

- a) A male subject who has not had a vasectomy must agree to use contraception as detailed in [Appendix 1](#) of this protocol during the treatment period and for at least 220 days (which includes the duration of relevant exposure plus the duration of sperm cycle) after the last study treatment administration and refrain from donating sperm during this period.
- b) Female subjects:
  - i) A woman of childbearing potential (WOCBP) is eligible to participate if she has a negative serum pregnancy test ( $\beta$ -human chorionic gonadotropin) at screening and a negative urine pregnancy test at Day 1 (see [Appendix 1](#)), is not breastfeeding, and agrees to follow the contraceptive guidance in [Appendix 1](#) during the treatment period and for at least 6 months after receiving the study treatment, and refrains from donating oocytes for assisted reproduction during this period. The female subject's selected form of contraception must be effective by the time the female subject enters into the study at Day 1 (eg, hormonal contraception should be initiated at least 12 Weeks before Day 1. For WOCBP, hormonal contraceptives must be used without schedule changes and in steady doses during the study treatment. Starting hormonal contraceptives during the study is not permitted. Use of any hormonal contraceptives containing drospirenone, chlormadinone acetate, or cyproterone acetate is prohibited unless part of a stable contraceptive regimen as described in [Section 6.5.1](#).
  - ii) A woman not of childbearing potential as defined in [Appendix 1](#) is eligible to participate in the study. A postmenopausal woman must have a follicles -stimulating hormone (FSH) test confirming nonchildbearing potential.

11. Willing to participate and capable of giving written informed consent, which must be personally signed and dated by the subject and obtained prior to any trial-related activities.
12. Willing to comply with all study procedures and must be available for the duration of the study.

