## 6.8 TREATMENT AFTER THE END OF THE STUDY

All subjects will return to the study site for the EOS (Day 281/Week 40) or ET visit for final safety and EOS assessments. After this visit, subjects should be treated according to the clinical judgment of the subject's physician. Care after EOS/ET will not be provided by AnaptysBio, Inc. Any SAE or pregnancy occurring through the EOS visit should be reported to the pharmacovigilance unit ([Section 8.2.1](#)) and followed up until an outcome is determined.

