### 7.2 SUBJECT DISCONTINUATION/WITHDRAWAL FROM THE STUDY

A subject may withdraw from the study at any time at his or her own request or may be withdrawn at any time at the discretion of the Investigator for safety, behavioral, compliance, or administrative reasons.

In case of early withdrawal from the study treatment, the subject will be required to attend an ET visit at the time the decision is made to stop study treatment early (see the SoA in [Section 1.3](#)). After completion of the ET visit, the subject should then return for a final follow-up EOS/ET visit approximately 12 weeks after receiving their last dose of study treatment. Subjects must be withdrawn from the study under the following circumstances, any SAE or AE which, in the opinion of the Investigator, warrant study discontinuation for safety reasons, or pregnancy occurring through the EOS, which should be followed up until outcome.

The following events are considered sufficient reasons for discontinuing a subject from the study treatment and/or the study:

- Pregnancy (refer to [Appendix 1](#) and [Section 8.2.1.8](#))
- Significant deviation/lack of compliance with protocol
- Any significant AE, laboratory abnormality, or other medical condition or situation occurs such that continued participation in the study would not be in the best interest of the subject in the opinion of the Investigator
- Disease progression which requires discontinuation of the study treatment
- Withdrawal of consent
- Lost to follow-up
- Use of any prohibited medication or treatment that in the opinion of the Investigator necessitates the subject being withdrawn (refer to [Section 6.5.2](#))
- Termination of the subject's participation by the Investigator or AnaptysBio

The reason for subject discontinuation or withdrawal from the study will be recorded on the eCRF.

If a subject withdraws from the study, he or she may request destruction of any samples taken and not tested, and the Investigator must document this in the study site study records.

See SoA ([Section 1.3](#)) for data to be collected at the time of study discontinuation and follow-up and for any further evaluations that need to be completed.

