**Collection of Pregnancy Information**

***Male subjects with partners who become pregnant***

The Investigator will attempt to collect pregnancy information on any male subject's female partner who becomes pregnant while the male subject is in this study. This applies only to male subjects who receive study treatment.

After obtaining the necessary signed informed consent from the pregnant female partner directly, the Investigator will record pregnancy information on the appropriate pregnancy form and submit it to the pharmacovigilance unit within 24 hours of learning of the partner's pregnancy. The female partner will also be followed to determine the outcome of the pregnancy. Information on the status of the mother and child will be forwarded to AnaptysBio. Generally, the follow-up will be no longer than 6 to 8 weeks following the estimated delivery date. Any termination of the pregnancy will be reported regardless of fetal status (presence or absence of anomalies) or indication for the procedure.

Any SAEs associated with the pregnancy in the male subject's partner should also be reported to the pharmacovigilance unit within 24 hours of the event using the back-up Paper Report Form.

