***Female subjects who become pregnant***

The Investigator will collect pregnancy information on any female subject who becomes pregnant while participating in this study. Information will be recorded on the appropriate form and submitted to the pharmacovigilance unit within 24 hours of learning of a subject's pregnancy. The subject will be followed to determine the outcome of the pregnancy. The Investigator will collect follow-up information on the subject and the neonate and the information will be forwarded to AnaptysBio. Generally, follow-up will not be required for longer than 6 to 8 weeks after the delivery date. Any termination of pregnancy will be reported, regardless of fetal status (presence or absence of anomalies) or indication for the procedure.

While pregnancy itself is not considered to be an AE or SAE, any pregnancy complication or elective termination of a pregnancy will be reported as an AE or SAE. A spontaneous abortion is always considered to be an SAE and will be reported as such.

Any poststudy pregnancy related SAE considered reasonably related to the study treatment by the Investigator will be reported to AnaptysBio as described in [Section 8.2.1.8](#). While the Investigator is not obligated to actively seek this information in former subjects, he or she may learn of an SAE through spontaneous reporting.

Any female subject who becomes pregnant while participating in the study will be withdrawn from the study.

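### Minor, cheap improvement: the pregnancy reporting window is tied to the end of the study, not the subject's last dose, so it can close before the required contraception period ends

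*Protocol*

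**What the plan says.** Three places in the protocol bear on how long pregnancies are reported or recorded.

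- **8.2.1.8** is the dedicated rule and the only text that asks the subject to report. It covers a female subject or a male subject's partner who "becomes pregnant during the study and up to 28 days after the end of the study". Once told, the investigator informs pharmacovigilance within 24 hours and follows Appendix 1.
- **6.8** is shorter: "Any SAE or pregnancy occurring through the EOS visit should be reported to the pharmacovigilance unit". It cross-refers to 8.2.1, where the longer rule sits.
- **Appendix 1** describes collection for a "female partner who becomes pregnant while the male subject is in this study" and for "any female subject who becomes pregnant while participating in this study".

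Contraception is required for longer. Section 5.1, criterion 10, asks men without vasectomy to continue "for at least 220 days (which includes the duration of relevant exposure plus the duration of sperm cycle) after the last study treatment administration", and women of childbearing potential "for at least 6 months after receiving the study treatment".

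The phrase used in 8.2.1.8 is also a defined term. Section 4.4 defines the end of the study as the last visit or procedure of the last subject. Where the protocol wants a per-subject limit, as in 8.2.1.4, it refers to the end of participation at the EOS/ET visit.

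**The concern.** The sections give different end points. A pregnancy beginning 20 days after a subject's EOS visit falls inside 8.2.1.8 but outside the literal wording of 6.8 and Appendix 1.

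The 28 days also hang on an ambiguous anchor. On one reading the window is fixed for each subject. On the other it depends on when other people finish, which a subject cannot know.

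On either reading, the request to report can lapse while the protocol still requires contraception. For men, the protocol says the contraception period includes the time of relevant exposure. No visit is scheduled after Day 281, so later detection depends on someone telling the site. The pregnancies most likely to be missed are those with a normal outcome that nobody mentions, and losing them would tilt the record of exposed pregnancies towards abnormal outcomes. Efficacy, eligibility and dosing are unaffected.

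**Working it through.** **Inputs**
- Last scheduled dose: Day 197, window ±4 days (Schedule of Activities).
- EOS visit: Day 281, window ±5 days (Schedule of Activities).
- Reporting extension: 28 days (8.2.1.8).
- Contraception after treatment: at least 6 months for women, at least 220 days for men without vasectomy (5.1).
- Assumptions: 6 months is 182 to 183 days, because the protocol gives no conversion, and it runs from the last dose.

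**Check on the plan's own interval.** 281 − 197 = 84 days = 12 weeks. This agrees with the 12 weeks from last dose to EOS in 6.3. Subjects who stop early are on the same footing, since under 7.2 "the subject should then return for a final follow-up EOS/ET visit approximately 12 weeks after receiving their last dose of study treatment".

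**Reading A: the end of the study means the subject's own EOS**

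Window closes at 84 + 28 = 112 days after the last dose.

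Gap = contraception period − 112.

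| | Contraception period (days) | Gap (days) | Share of period |
|---|---|---|---|
| Women | 182 to 183 | 70 to 71 | 70/182 = 38.5% to 71/183 = 38.8% |
| Partners of men | 220 | 108 | 108/220 = 49.1% |

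Visit windows move this by about 9 to 10 days either way:
- EOS minus last dose runs from 276 − 201 = 75 to 286 − 193 = 93 days. Adding 28 gives 103 to 121.
- Women: 182 − 121 = 61 to 183 − 103 = 80 days.
- Partners of men: 220 − 121 = 99 to 220 − 103 = 117 days.

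If a site stopped at EOS, on the literal wording of 6.8, the nominal gaps would be 182 − 84 = 98 to 183 − 84 = 99 days (women) and 220 − 84 = 136 days (partners of men).

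**Reading B: the end of the study as defined in 4.4**

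Let L be the days from the subject's own EOS to the last subject's last visit. The documents do not give L, so a range is assumed.

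Gap = max(0, 182 − 112 − L) for women and max(0, 220 − 112 − L) for partners of men.

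| L (days) | Women (at 182 days) | Partners of men |
|---|---|---|
| 0 | 70 | 108 |
| 30 | 40 | 78 |
| 60 | 10 | 48 |
| 90 | 0 | 18 |
| 108 or more | 0 | 0 |

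The gap closes for women at L = 70 (71 if 6 months is 183 days) and for partners of men at L = 108.

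**The case against.** Several arguments cut the point down, and most of them stand.

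- **No rule is broken.** No section says reporting must last as long as contraception. That stands, and it makes this a suggestion.
- **In practice one rule governs.** Section 6.8 deals with care after the study, does not say that only those pregnancies count, and sends the reader to 8.2.1. A site following the reference reaches the longer window, and 8.2.1.8 sends every reported pregnancy to the Appendix 1 procedures. This weakens the inconsistency, but the wording still differs.
- **Section 7.2 is not a further reporting cut-off.** A reader might take "pregnancy occurring through the EOS, which should be followed up until outcome" as one. It is part of a withdrawal rule, and withdrawal cannot happen after EOS, so the limit is inherent.
- **The full gaps need Reading A.** Section 8.2.1.8 uses the phrase that 4.4 defines at trial level. On that reading, early finishers have no gap, and the share of subjects affected is unknown.
- **Much is captured anyway.** The instruction to inform pharmacovigilance within 24 hours of a reported pregnancy carries no time limit of its own. Abnormal outcomes are SAEs, and SAEs considered reasonably related that come to light later must be notified (8.2.1.4, Appendix 1).
- **Late exposure is low.** With the half-life of about 28 days in 4.3, 112 days is four half-lives, leaving about 0.5^4 = 6% of drug if decline is first-order. The 220 days also include a sperm cycle, so the 108 days are not all relevant exposure. Against that, exclusions 19 and 20 refer to five half-lives when washing out other drugs, which here would be 5 × 28 = 140 days.
- **Other documents may ask for more.** The consent form, Safety Reporting Instructions and Safety Management Plan were not available. They may close the gap in practice, but they would not change the protocol text.

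**Conclusion.** The point holds as a minor, low-cost improvement to safety capture. The reporting window in 8.2.1.8 rests on an ambiguous anchor, differs in wording from 6.8 and Appendix 1, and can close before the contraception period does.

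The size depends on the reading. Per subject, the nominal gap is 70 to 71 days for women and 108 days for partners of men without vasectomy, and it applies to anyone on schedule. With the 4.4 definition it applies only to later finishers and shrinks to zero as L grows. Both rest on taking 6 months as 182 to 183 days from the last dose.

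A reader might infer that every subject goes uncovered for those periods, or that late pregnancies would be lost. The documents do not support either: the first requires the per-subject reading, and the second ignores the duty to pass on what the investigator is told. Nor do they support calling the mismatch with contraception an error.

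The expected number of affected pregnancies is small, with about 120 subjects and highly effective contraception required of women of childbearing potential. It cannot be estimated from the documents.

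**What to change.** In 8.2.1.8, replace the 28-day extension with a window counted from the subject's own last dose: at least 6 months for female subjects and 220 days for partners of male subjects. On the nominal schedule this is EOS plus 98 to 99 days (182 − 84 to 183 − 84) and EOS plus 136 days (220 − 84). Make 6.8 and the Appendix 1 collection wording match. Leave the withdrawal rule in 7.2 as it is. Confirm that the consent form asks subjects to report a pregnancy within that window.

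The cost is protocol wording, consent wording if it is not already there, and a little more pregnancy follow-up after the last visit. No visit or procedure is added.

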#### 8.2.1.9 TREATMENT OF OVERDOSE

For this study, any dose of imsidolimab or placebo administered in a volume exceeding the planned dosing detailed in [Table 3](#) (Dose Strength[s]/Dosage Level[s]) will be considered an overdose.

In the improbable event of a suspected overdose, the following procedures should be executed:

- Administration is to be discontinued.
- The subject is to be monitored clinically.
- Supportive measures are to be undertaken as clinically indicated.
- Electrocardiography and clinical laboratory evaluations (ie, blood glucose, hepatic enzymes, creatinine, blood urea nitrogen, creatine kinase (CK), and complete blood count) are to be performed and followed until all values return to Baseline levels and AEs subside, if applicable.

No information on overdose, maximum tolerated dose, or dose-limiting toxicities for imsidolimab has been established at this time and since there are no known antidotes for imsidolimab, the treatment of overdose is at Investigator's discretion.

In the event of an overdose, the Investigator should:

1. Contact the Medical Monitor immediately.
1. Closely monitor the subject for any AE/SAE and laboratory abnormalities and follow-up until resolution.
2. Obtain a serum sample for PK analysis soon after the dose for SC administration.
3. Document the quantity of the excess dose as well as the duration of the overdose in the eCRF.

Decisions regarding dose interruptions will be made by the Investigator in consultation with the Medical Monitor based on the clinical evaluation of the subject.

#### 8.2.2 HEIGHT AND WEIGHT

Height (cm) and weight (kg) will be collected to calculate the body mass index (BMI). Height and weight will be measured at the time points specified in the SoA ([Section 1.3](#)).

